## 7. HYPOTHESIS AND OBJECTIVES

### 7.1. Primary objective:

- To describe the baseline clinical characteristics of the population of patients who are long-term responders to axitinib and to identify clinical factors associated with a long-term response to axitinib.

*For the study, “long-term responders to axitinib” has been defined as patients with progression-free survival [PFS] of at least 9 months with the drug, and “patients refractory to axitinib” has been defined as patients with disease progression in the first assessment after the start of treatment [estimated PFS  $\leq$ 3 months]*

To meet the study objective, two groups of patients with extreme response to the drug will be compared: a group of patients with long-term responses to the drug (group of long-term responders to axitinib) compared to a group of patients with disease progression in the first assessment after starting treatment (group of patients refractory to axitinib), in which the association of the following clinical factors will be analysed with the benefit of the treatment;

- Age ( $\leq$ 65 years and  $>$ 65 years)
- Baseline ECOG/PS at the start of treatment for each line (0, 1 and  $\geq$ 2)
- Number of previous treatment lines (1, 2 and  $\geq$ 3)
- Previous nephrectomy (yes and no)
- MSKCC risk group (favourable, intermediate and poor)
- IMDC risk group (favourable, intermediate and poor)
- Change in the MSKCC or the IMDC risk group with respect to the previous line (yes vs no);
- Histology (100% clear cells, main component of clear cells, main component of non-clear cells, 100% non-clear cells).

- Duration of first-line with a TKI ( $\geq 12$  months,  $\leq 6$  months;  $\leq 3$  months)
- Better response with the TKI received in first-line (CR/PR, SD, DP)
- Number of metastatic locations (1, 2 and  $\geq 3$ );
- Site of metastases (CNS metastases [yes vs no]; lymph nodes [yes vs no]; lung [yes vs no]; liver [yes vs no]; bone [yes vs no])
- Baseline LDH levels  $\leq 1.5 \times \text{ULN}$  (yes vs no)
- Baseline Hgb levels  $> \text{LLN}$  (yes vs no)
- Baseline corrected  $\text{Ca}^{++}$  levels  $\leq 10$  mg/dl (yes vs no)
- Baseline neutrophil levels  $\leq \text{ULN}$  (yes vs no)
- Baseline platelet levels  $\leq \text{ULN}$  (yes vs no)
- Neutrophil/lymphocyte ratio  $\leq 3$  (yes vs no)
- Smoking habits (smoker, non-smoker or ex-smoker)

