### Study population

The eligible patient population for this study includes any patient with advanced or metastatic renal cell carcinoma who has been treated with axitinib for at least 9 months or whose best response to this treatment has been DP.

The requirements for a patient's inclusion are:

1. These patients had to receive axitinib as second-line treatment or further line, according to its Summary of Product Characteristics. Two groups exhibiting extreme responses to the drug will be compared: one group of patients showing no evidence of disease progression for at least 9 months after the start of treatment with axitinib versus a group of patients showing disease progression while taking the drug at the first response assessment.
2. Collection of clinical, safety and response data in patients with advanced renal cell carcinoma.

The study is expected to be conducted in at least 30 sites throughout Spain in order to reach the maximum number of study patients.

The study will start at each site after the agreement with the site is signed and all study documentation and information on the procedures and objectives of the study have been received by the person appointed by the sponsor.

Recruitment will be competitive between all participating sites. All the patients at a particular site who meet the inclusion criteria during the recruitment period may be enrolled. The recruitment period will have a maximum of three months from the opening of the last study site. No patient follow-up will be carried out after their inclusion in the study.

Patients will be considered evaluable if they meet the inclusion criteria and do not meet the exclusion criteria, and have received at least one dose of axitinib prior to their inclusion in the study.

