- IC4: *Treatment with axitinib, as second-line or further line treatment and with progression-free survival PFS of 9 months or more or with disease progression at the first response assessment.*

It must be verified that in "Treatment with axitinib", "Treatment line in which it has been received" is  $\geq 2$ .

It must be verified that the patient meets one of the following two conditions:

- "*Progression-free survival PFS of 9 months or more*": the time from the start of treatment with axitinib to disease progression or death by any cause is  $\geq 9$  months (see definition of PFS in section 7. Definition of variables).

or

- "*Disease progression at the first response assessment*": PD has been indicated in "Treatment with axitinib/ Best response to treatment".

If there is a contradiction between the binary variables and the information shown in the CRF, the latter shall be assumed valid.

A list of candidate patients who are non-evaluable must be made, and after approval or rectification by the study sponsor/coordinator, the list of non-evaluable patients who will be excluded from the analyses will be closed.

The sponsor will be informed of the number of non-evaluable study patients for the analysis and the reasons for non-inclusion, for consultation and confirmation prior to starting the analyses.

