**Cohort treatment/labelling**

For the study, “long-term responders to axitinib” have been defined as patients with a PFS for at least 9 months with the drug, and “refractory patients to axitinib” have been defined as patients with disease progression in the first assessment since the initiation of treatment (estimated PFS  $\leq 3$  months).

See point 5.2. *subgroups*, and in group 7 *Definition of variables and objectives*, how these groups are defined in terms of CRFs variables and algorithmic conditions of computer programming for the patient’s classification.

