#### **5.2 SUBGROUPS**

For some of the study objectives, the following two groups of patients with extreme responses to the drug are defined (see definition in point 7. Definition of variables):

- “Long-term responders to axitinib”: Patients who have a PFS of at least 9 months with the drug.
- “Patients primary refractory to axitinib”: Patients with disease progression at the first assessment after the initiation of treatment (estimated PFS  $\leq 3$  months). It means, patients with best response to axitinib=PD.

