 $(\text{Dose increase date or Dose reduction date} - \text{Start date of treatment with axitinib}) / 30.4375$
  - Duration (months) of subsequent treatments =  
 $(\text{Date of end of subsequent treatment or of latest follow-up if not suspended} - \text{Date of start of subsequent treatment}) / 30.4375$ . In the case of several subsequent treatments per patient, proceed as follows: the duration in months of each of the subsequent treatments will be calculated (from the start date to the end date or last check if it continues). This will be done for all subsequent treatments and then proceed to make the sum per patient of all durations of subsequent treatments

- Progression-Free Survival (PFS, in months) =  
 (Date of Disease Progression on treatment with axitinib or death from any cause – Date of start of treatment with axitinib) / 30.4375  
 If there is no progression or death, the case is censored as  
 PFS (months) = (Date of latest follow-up – Date of start of treatment with axitinib) / 30.4375
- Time to progression (TTP, in months) =  
 (Date of Disease Progression – Date of start of treatment with axitinib) / 30.4375  
 If there is no progression, the case is censored as  
 TTP (months) = (Date of latest follow-up – Date of start of treatment with axitinib) / 30.4375
- Overall Survival (OS, in months) = (Date of death – Date of start of treatment with axitinib) / 30.4375  
 If death has not occurred, the case is censored as  
 Overall Survival (OS, in months) = (Date of latest follow-up – Date of start of treatment with axitinib) / 30.4375
- Overall Survival since the start of first-line treatment (OS, in months) = (Date of death – Date of start of first-line treatment) / 30.4375  
 If death has not occurred, the case is censored as  
 Overall Survival (OS, in months) = (Date of latest follow-up – Start date of first treatment) / 30.4375
- Patient subgroups
  - A-Long-term responders: comprising patients with PFS  $\geq 9$  months.
  - B-Refractory (primary): comprising patients with best response to treatment = PD. This date is collected in the CRF form “axitinib treatment”.
- MSKCC risk group (described in appendix 11.1.). It will be analysed “Before the beginning of the first line”. These calculations will be performed on patients who have data on all the variables involved (in the case of a patient who does not have data on all the variables but has > 2 factors, it will be classified in the “Poor” risk group.

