## 7.1 PRIMARY OBJECTIVE

In order to meet the study's primary objective, the baseline clinical characteristics of two patient groups with extreme response to the drug will be compared: A group of patients with long-term responses to the drug (long-term responders to axitinib) versus a group of patients with disease progression at the first assessment after the initiation of treatment (group of patients refractory to axitinib).

The classification (in long-term responders or refractory patients) will be based on PFS (in months), as indicated in section 5.2.

It will be shown the following descriptive tables:

- “Long responder” patient (Yes, No). “Long responding patient” is defined if he / she has an PFS  $\geq 9$  months (during axitinib treatment). The 95% CI will be displayed.
- PFS in long responding patients. Only the descriptive analysis of the time in months and the CI for the average, will be shown.
- “Refractory” patient (Yes, No). "Refractory patient" is defined if there is a better response to treatment = PE (to axitinib treatment). 95% CI will be shown.
- PFS in refractory patients. Only the descriptive analysis of the time in months and the CI for the average will be shown.
- Patient group (Long respondent, refractory). It is defined in section 5.2. IC95% will be displayed

At the same time, In addition to comparisons of baseline clinical characteristics between the groups (long-term responders, refractory patients), an association analysis of the following factors with the study groups will be performed:

- Age with respect to first visit ( $\leq 65$  years and  $> 65$  years).
- Age with respect to first diagnosis ( $\leq 65$  years and  $> 65$  years).
- Age with respect to start of axitinib ( $\leq 65$  years and  $> 65$  years).
- Baseline ECOG/PS and at the initiation of first line treatment (0, 1 and  $\geq 2$ ).
- Baseline ECOG/PS and at the initiation axitinib treatment (0, 1 and  $\geq 2$ ).
- Baseline ECOG/PS and at the end of axitinib treatment (0, 1 and  $\geq 2$ ).
- Number of previous treatment lines
- Number of previous treatment lines (1, 2 and  $\geq 3$ )
- Previous nephrectomy (yes and no)
- MSKCC (or IMDC) risk group in all moments in which it is analysed during the study (favourable, intermediate and poor)

- Histology (100% clear cells, primarily clear cells, primarily non-clear cells, 100% non-clear cells)
- Duration of first-line treatment

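### The PFS rule that defines long-term responders can credit time off axitinib, against the plan's own on-drug wording

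*SAP*

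**What the plan says.** **The operative rule.** SAP section 7 runs PFS from axitinib start to "Date of Disease Progression on treatment with axitinib or death from any cause". Without either event, PFS is censored at latest follow-up. The subgroup rule follows: "A-Long-term responders: comprising patients with PFS" of 9 months or more. The IC4 check in SAP 2.1 (Analysis population) requires that "the time from the start of treatment with axitinib to disease progression or death by any cause is" at least 9 months and refers to the section 7 PFS. It adds no test of time on drug.

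**Wording that ties the 9 months to the drug.**
- Protocol 7.1: "patients with progression-free survival [PFS] of at least 9 months with the drug".
- SAP 2.1 (Cohort treatment/labelling): "patients with a PFS for at least 9 months with the drug".
- SAP 5.2: "Patients who have a PFS of at least 9 months with the drug".
- SAP 7.1 defines the long responder by a PFS of at least 9 "months (during axitinib treatment). The 95% CI will be displayed".
- SAP 2.1 (Study population) describes an eligible patient as one "who has been treated with axitinib for at least 9 months or whose best response to this treatment has been DP". Protocol 8 and 8.2 also speak of at least 9 months of treatment.

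**Wording that agrees with the formula.** The primary objective in the protocol abstract and SAP 2.2 count from the start of the drug. So does the two-group description in Protocol 8.2 and SAP 2.1 (Study population).

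**Related rules.** SAP section 6 records toxicity and other reasons, besides progression, for stopping axitinib. SAP 7.2 says progression dates are not available for treatments after axitinib. SAP 7.2 also censors sunitinib PFS, when there is no progression, at the start of axitinib, which is the next drug.

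**The concern.** Long-responder status is the outcome of the primary comparison and the dependent variable of the logistic regression. It also decides, through IC4, who is evaluable. If the group includes patients who left axitinib early and stayed alive on no treatment or on another drug, the factors found will partly reflect general prognosis instead of benefit from axitinib, which is what the study sets out to examine.

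About 60 patients are expected, at roughly 2:1, and factors are kept by p-value thresholds (SAP 7.1). Membership of the larger group should therefore mean what the objective says it means.

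**Working it through.** The plan gives no figure for this point, so there is nothing to reproduce. The check applies the rule to constructed patients and then sizes the effect under stated assumptions.

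**1. The rule applied (months from axitinib start, no progression recorded)**

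| Patient | Stop | Next drug | Last seen alive | PFS by SAP section 7 | Class as written |
|---|---|---|---|---|---|
| A | 2 | 3 | 14 | 14 | Long responder |
| B | 4 | none | 12 | 12 | Long responder |

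Neither was on axitinib for 9 months. If follow-up were cut at the next drug, A would have 3 months observed and B would still have 12. If it were cut at axitinib stop, they would have 2 and 4. Those shorter times are censored: they leave 9-month status unknown and do not show progression before month 9.

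**2. How many patients (illustrative)**

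Inputs from the documents:
- 60 patients at 2:1, so 40 long responders (Protocol 8.5 and abstract).
- Median PFS 6.7 months, or 4.8 after sunitinib, and median OS 20.1 months (Protocol 6.1.6).
- 4% withdrawal for related adverse events (Protocol 6.1.7), given without timing or progression status.

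Assumptions: exponential times; stop at month s = 2 or 5; a share r = 0 or 0.5 with progression recorded between stop and month 9.

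- P(PFS ≥ 9) = exp(−ln2 × 9/6.7) = 0.394, or exp(−ln2 × 9/4.8) = 0.273.
- q, the chance that an early stopper reaches a formula PFS of 9 months, = exp(−ln2 × (9 − s)/20.1) × (1 − r). For s = 2 this is 0.786 (r = 0) or 0.393 (r = 0.5). For s = 5 it is 0.871 or 0.436.
- Share of long responders affected = d·q / [d·q + (1 − d)·P(PFS ≥ 9)], where d is the proportion stopping early without progression.
- Low end at d = 0.04: 0.04 × 0.393 / (0.04 × 0.393 + 0.96 × 0.394) = 0.040, or 1.6 of 40.
- High end at d = 0.04: 0.04 × 0.871 / (0.04 × 0.871 + 0.96 × 0.273) = 0.117, or 4.7 of 40.
- At d = 0.02 the range is 0.8 to 2.4. At d = 0.08 it is 3.2 to 8.7.

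The true lower limit is zero, because sites that read eligibility as 9 months of treatment would not have enrolled such patients.

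**3. Effect on an odds ratio**

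Take a factor present in 60% of true long responders and 27.3% of refractory patients: OR = (0.60/0.40)/(0.273/0.727) = 4.0. Suppose m of the 40 in fact resemble refractory patients. The observed prevalence is then (1 − m/40) × 0.60 + (m/40) × 0.273.

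- m = 1: OR 3.87.
- m = 2: OR 3.74.
- m = 4: prevalence 0.567, OR 3.50.

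**4. Precision with and without four patients**

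- 40 vs 20: SE(log OR) = √[1/(40 × 0.60 × 0.40) + 1/(20 × 0.273 × 0.727)] = 0.597, 95% CI 1.24 to 12.89.
- 36 vs 20: SE = 0.606, 95% CI 1.22 to 13.13.

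**The case against.** **The SAP names its algorithm.** SAP 2.1 (Cohort treatment/labelling) and 5.2 send the reader to section 7 for the definition, and Protocol 8.3 leaves operational definitions to the SAP. A reader might infer that nothing governs and that any grouping is possible. The documents do not support that: the section 7 formula is the working rule, and the IC4 check imports it. What stands is that the on-drug parenthesis in 7.1 lies inside section 7 itself and contradicts the formula.

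**Counting progression or death whatever comes next is a recognised PFS convention.** A reader might infer that censoring at the next therapy must become the primary rule. The documents do not establish this. The sunitinib definition shows the SAP using such a rule elsewhere, but no axitinib passage calls for it, and it would leave patient B a long responder.

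**Early stoppers are not failures.** A reader might move them out as having PFS under 9 months. A censoring time below 9 months does not show that.

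**The effect may be small or nil.** This stands. The 4% is only an anchor, and the CRF progression field could capture progression after stop. A reader might also infer that these patients would decide which factors are significant. With 40 vs 20, significance shifts readily when any few patients are added, correctly classified or not, so that cannot be pinned on this rule.

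**Axitinib duration is compared by group (SAP 7.1).** That may reveal short durations but reclassifies no one.

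**Conclusion.** The point holds as a mismatch between the operative rule and the stated meaning of the group, and it should be fixed. As written, the rule can class a patient as a long-term responder to axitinib on time spent off it. The SAP is also unclear on progression recorded after axitinib stop: section 7 limits PFS progression to that on axitinib, but its time-to-progression definition has no such limit.

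The size is uncertain: roughly 0 to 5 of 40 if the 4% rate applied, under the exponential and recording assumptions above. An odds ratio of 4.0 would fall to about 3.5 with four such patients, if they fully resembled refractory patients. That shift is small against a 95% CI of 1.24 to 12.89. The documents do not show that any patient is misclassified or that the primary result is wrong.

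**What to change.** 1. Reconcile the section 7 algorithm and the IC4 check with the on-drug wording in Protocol 7.1, 8 and 8.2 and in SAP 2.1, 5.2 and 7.1. State whether progression recorded after axitinib stop counts, for both PFS and time to progression.
2. List every patient with PFS of at least 9 months but axitinib duration under 9 months, with stop reason and start date of the next therapy.
3. Repeat the primary comparison and logistic regression without long responders who stopped axitinib, or started a later systemic therapy, before month 9 without recorded progression. Treat them as not classifiable, not as failures.
4. Label this post hoc, because SAP version 3 followed a draft of results (SAP section 1), and report it beside the grouping as written. Next-therapy censoring should not be imposed as the only primary rule.

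**Cost.** SAP wording and some programming from dates the CRF already holds. A protocol amendment is needed if the reconciliation is a major change to the primary definitions (Protocol 8.7). A few patients leave the sensitivity analysis. Losing four of 40 widens the interval around an odds ratio of 4.0 only from 1.24–12.89 to 1.22–13.13.

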### **8.2.1. Inclusion Criteria**

Patients must meet all the inclusion criteria below to be eligible for inclusion in the study:

1. *Evidence of a personally signed and dated informed consent form indicating that the patient (or his/her legal representative) has been informed of all aspects relevant to the study. Informed consent will only be obtained from patients who are still alive.*
2. *Aged 18 or over.*
3. *Histologically confirmed diagnosis of advanced kidney cancer, with at least one radiological evaluation of the disease in accordance with RECIST 1.1 criteria*

4. *Treatment with axitinib as second-line or later with a PFS equal to or greater than 9 months, or with disease progression in the first response assessment*

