### **8.3. Variables**

For this observational study, the following variables will be recorded: demographic, medical history (including date and stage of disease at diagnosis and at progression), surgical treatment, histology, blood count and blood biochemistry, first-line treatments, associated adverse events, clinical efficacy and history of treatment with axitinib, including treatment line (second, third, etc.), dose, reason and date of start of treatment, disease risk criteria before onset, comorbidities, associated adverse events, concomitant medication and subsequent treatments, as well as the patient’s condition (alive, deceased) and the last date on which contact was made.

A complete description of the variables, including the operational definitions, will be detailed in the Statistical Analysis Plan of the study.

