    - Has treatment with axitinib been discontinued? (Yes/No)
      - If yes, specify:
        - End-of-treatment date
        - Reason for suspension of treatment (DP/Toxicity/Other, specify)
    - Risk criteria at discontinuation of treatment with axitinib

- 
- Time from first diagnosis to systemic treatment less than 1 year (Yes/No/Unknown)
    - ECOG/PS (current status) (Yes/No/Unknown)
    - LDH >1.5 x ULN (Yes/No/Unknown)
    - Haemoglobin < LLN (Yes/No/Unknown)
    - Corrected calcium >10 mg/dl (Yes/No/Unknown)
    - Presence of 2 or more metastatic sites (Yes/No/Unknown)
    - Platelets > ULN (Yes/No/Unknown)
    - Neutrophils > ULN (Yes/No/Unknown) (value)
  - Has there been disease progression? (No/Yes, specify date)
  - Best treatment response (CR, PR, SD, DP/Not evaluable).
    - Date of the best response obtained
  - Starting dose (5 mg/12 h; 2 mg/12 h; 3 mg/12 h; 7 mg/12 h; 10 mg/12 h)
  - Has the dose been modified? (Yes/No)
    - If yes, specify:
      - Increased/Reduced
      - Dose modification date
      - Reason for dose modification
      - New dose (5 mg/12 h; 2 mg/12 h; 3 mg/12 h; 7 mg/12 h; 10 mg/12 h; other, specify mg/h)
  - Adverse events
    - Adverse events (Anaemia; Asthenia; Fatigue; Diarrhoea; Dysphonia; Elevated ALT/GPT; Elevated AST/GOT; Elevated Bilirubin; Elevated Creatinine; Elevated Haemoglobin; Elevated Lipase; Hypercalcaemia; Hypertension; Hypocalcaemia; Hypophosphatemia; Hypothyroidism; Lymphopenia; Mucositis; Nausea; Neutropenia; Proteinuria; Rash; Hand-foot syndrome; Thrombocytopenia; Vomiting, Other, specify).
    - Worst grade according to CTCAE
    - Cycle in which the worst grade occurred
    - Related to treatment (Yes/No)
    - Serious AE? (Yes/No), if yes, specify
      - Reason (Results in death/ Is life threatening/ Leads to hospitalisation or prolongation of hospitalisation/ Causes persistent or significant disability or incapacity/ Causes a congenital anomaly or birth defect/ Is medically significant).
  - Subsequent treatments
    - Has the patient received any subsequent treatment? (Yes/No)
      - If yes, specify
        - Drug received
        - Starting dose
        - Treatment line
        - Start date

- End date
- Ongoing
- Best response attained (CR, PR, SD, DP/Not evaluable)
- Reason for discontinuation (DP/Toxicity/Other, specify)
- Vital status
  - Date of last follow-up
  - Status (Alive/Death)
    - If Death, specify
      - Date of death
      - Cause of death (DP, Other, specify)

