## 7 DEFINITION OF VARIABLES AND OBJECTIVES

In addition, the following variables will be calculated from the CRF data:

NOTE: In patients with dates after the date of the IC visit / signature, the date of the IC visit / signature has been considered as the date of the last check. Due to the retrospective nature of the study, no data can be collected after the patient was included in the IC study / signature.

- Age (years) of patient at time of visit= (Visit date – Date of birth) / 365.25
- Age (years) at first diagnosis= (Date of first diagnosis – Date of birth) / 365.25
- Age (years) at the initiation of axitinib= (start date of axitinib – Date of birth) / 365.25
- Number of metastatic locations = sum (Lymph nodes, CNS, Hepatic, Pulmonary, Bone, Other).
- • Neutrophil / lymphocyte ratio. It will be categorized as follows:  $\leq 3$ ,  $> 3$ . "Before the beginning of the first line" and "At the beginning of treatment with axitinib" will be analyzed. This ratio is not calculated on axitinib suspension because there is no current lymphocyte value data in that part of the CRF.
- Time (months) between first diagnosis and nephrectomy = (Date of nephrectomy – Date of first diagnosis) / 30.4375. A list with the information (site, patient, date of first diagnosis, date of nephrectomy and the calculated time) in cases in which the time is negative (with date of nephrectomy before or equal to date of first diagnosis) will be displayed, and these cases will not be included in the descriptive analysis
- Time (months) between first diagnosis and radiotherapy = (Date of radiotherapy – Date of first diagnosis) / 30.4375. A list with the information (site, patient, date of first diagnosis, date of radiotherapy and the calculated time) in cases in which the time is negative (with date of radiotherapy before or equal to date of first diagnosis) will be displayed, and these cases will not be included in the descriptive analysis.
- Time (months) between first diagnosis and 1st-line treatment = (Date of the initiation of 1st-line treatment – Date of first diagnosis) / 30.4375. A list with the information (site, patient, date of first diagnosis, date of 1st-line treatment and the calculated time) in cases in which the time is negative (with date of 1st-line treatment before or equal to date of first diagnosis) will be displayed, and these cases will not be included in the descriptive analysis

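### Event-free PFS and TTP run to last contact, not to the last tumour assessment, so a patient whose imaging lapsed before month 9 can be classed as a long-term responder

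*SAP*

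**What the plan says.** SAP section 7 gives PFS in months from axitinib start to progression or death. For patients without an event the wording is "If there is no progression or death, the case is censored as", and the formula supplied for them is "PFS (months) = (Date of latest follow-up – Date of start of treatment with axitinib) / 30.4375". TTP is handled alike: "TTP (months) = (Date of latest follow-up – Date of start of treatment with axitinib) / 30.4375". The same follow-up date censors OS.

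In the variable list of SAP section 6, "Date of last follow-up" is a vital-status item. Protocol section 8.3 lists it beside alive/deceased status as "the last date on which contact was made". The note at the head of SAP section 7 deals with dates later than consent: "the date of the IC visit / signature has been considered as the date of the last check". For axitinib, section 6 lists a progression date and a best-response date, but no date of last tumour assessment.

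The imaging condition for entry (Protocol section 8.2.1) is a confirmed diagnosis "with at least one radiological evaluation of the disease in accordance with RECIST 1.1 criteria", with no timing attached. Protocol section 8.2 leaves assessments to each site's routine.

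The group rule in SAP section 7 reads "A-Long-term responders: comprising patients with PFS" of 9 months or more. It sets no condition on event status or on imaging.

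**The concern.** A last contact shows that a patient was alive. It does not show that the disease had not progressed. When imaging stopped before month 9 and contact continued past it, the SAP formula credits progression-free time that nobody observed.

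PFS of at least 9 months does three jobs in this study: it is part of inclusion criterion 4, it labels one of the two groups in the primary comparison, and it is therefore the outcome in the logistic regression. SAP section 7.1 also reports PFS in long responders as a plain descriptive mean with a confidence interval, so a contact date enters that result as if it were an observed event time.

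The error has one direction. A scan is itself a contact, so last contact cannot come before the last scan within the observation period. Event-free times can only be lengthened, and the long-responder group can only be enlarged by patients whose status at month 9 is unknown.

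**Working it through.** The plan gives no figure that depends on this rule (the sample size calculation is declared not applicable), so there is nothing to reproduce. The check applies the SAP formula to a constructed patient and then illustrates the size.

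**Step 1: the formula.** Axitinib starts on 1 January 2017. The last clear scan is on 3 April 2017 (day 92) and the last contact on 5 October 2017 (day 277). There is no recorded progression.

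- SAP rule: 277 / 30.4375 = 9.10 months, so long-term responder.
- Censoring at the last assessment: 92 / 30.4375 = 3.02 months, so 9 months is not shown. The patient is in neither group unless best response was progression.

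The same result follows for a patient who stopped for toxicity and was not scanned again. SAP section 7.1 ties the long-responder definition to the time on axitinib, but the section 7 formula does not implement that.

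**Step 2: who can be affected.** Only event-free patients whose last scan was before month 9 and whose last contact was after it. The documents give no count.

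**Step 3: illustration.** Let t be the month of the last clear scan. Assume an exponential hazard λ = ln 2 / median. The chance of an event between t and month 9 is 1 − exp(−λ(9 − t)). The medians come from Protocol section 6.1.6: 6.7 months overall, 4.8 after sunitinib and 12.1 after cytokines. For 6.7 months, λ = 0.1035 per month.

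| Last clear scan | Median 6.7 | Median 4.8 | Median 12.1 |
|---|---|---|---|
| Month 3 | 46% | 58% | 29% |
| Month 6 | 27% | 35% | 16% |
| Month 8 | 10% | 13% | 6% |

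The hazard includes deaths, whereas these patients were alive at last contact, so the figures somewhat overstate unseen progression.

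**Step 4: regular scanning.** Assume scans every 12 weeks (84 / 30.4375 = 2.76 months), uniform timing, and last contact less than one interval after the last scan. The mean gap from last scan to month 9 in the affected subset is then 2.76 / 3 = 0.92 months, and 1 − exp(−0.1035 × 0.92) ≈ 9%. In this setting the next scan is due after last contact, hence after month 9. Any progression it showed would be dated after month 9 and the label would stand.

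**Step 5: weight of one patient.** About 60 patients at about 2:1 gives 60 × 2/3 = 40 long-term responders. One misclassified patient is 1/40 = 2.5% of that group.

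**The case against.** The best counter-argument is that regular scanning makes the problem nearly vanish, as step 4 shows. A strict rule demanding a scan at or after month 9 would also be uneven. Take two patients with clear scans at month 7. One is followed to a progression scan at 9.8 months and stays a long responder; the other consents at 9.1 months and is dropped. This stands, and it is why the fix allows a window.

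A reader might take the whole gap from last scan to last contact under 12-week scanning (about 1.4 months on average, up to 2.8) and conclude that 13% to 25% of the exposed patients are misclassified. The documents do not support that. They state no scan interval; the relevant gap ends at month 9, not at last contact; the hazard counts deaths; and the next regular scan would be dated after month 9 in any case. Nor do they support the inference that the long-responder group is heavily contaminated. Protocol section 9.1 expects many patients to have died before inclusion, and patients followed well past month 9 will often have a later scan.

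It can also be said that investigators verify eligibility and that the sponsor or coordinator closes the list of non-evaluable patients. That does not cure the rule. Under SAP section 2.1, CRF data override the yes/no eligibility item when the two conflict, and the CRF holds no date that would expose lapsed imaging.

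Finally, the IC4 check in SAP section 2.1, taken literally, asks for progression or death at 9 months or later, which would leave out event-free patients altogether. It refers to the section 7 definition, however, and that includes censored times. The two wordings disagree. Remaining on axitinib does not settle the matter either: Protocol section 6.1.6 notes that pivotal-trial patients could continue after RECIST progression.

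**Conclusion.** The point holds for the censoring rule and for the label built on it. The stated rule can class as a long-term responder a patient with about 3 months of documented progression-free time, and any error in event-free PFS and TTP is upward. Patients with progression or death dated at 9 months or later are not affected.

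The extent is unknown. It depends on how often imaging lapsed before month 9 while contact continued, and the documents are silent on this. The percentages in the table describe the risk for one such patient under an assumed exponential hazard. They are not a share of the cohort. The case for changing the rule rests on its one-sidedness, its place in the primary comparison and the low cost of correction, not on a demonstrated large bias.

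**What to change.** 1. For each event-free patient, collect the date of the last tumour assessment without progression. The third SAP version followed draft results, and data collection was scheduled to close on 30 December 2018, so a data query to sites is more realistic than a new CRF field.
2. Censor PFS and TTP at that date. Keep last contact for OS.
3. Label an event-free patient a long-term responder only with a progression-free assessment at or after month 9, or within a stated window of one scan interval, so that regularly scanned patients are not lost because of when consent fell. Write this as its own rule, because a patient accepted through the window would have censored PFS slightly below 9 months.
4. Align the IC4 check in SAP section 2.1 with section 7, saying explicitly how event-free patients qualify.
5. If the date can no longer be obtained, run a sensitivity analysis of the primary comparison without event-free patients whose last contact is only shortly after month 9, with the cut-off stated, and report the limitation. This needs no new data but misses patients with lapsed imaging and long later contact.

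The cost is one date or query per event-free patient, plus SAP wording. A few borderline patients may leave the long-responder group, and median PFS and TTP may shorten slightly.
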